14.2 Clinical Trial in Patients Switching from Imiglucerase Treatment to ELELYSO

The safety and efficacy of ELELYSO were assessed in 31 patients (26 adult and 5 pediatric patients) with Type 1 Gaucher disease who were switched from imiglucerase to ELELYSO. The trial was a 9-month, multi-center, open-label, single arm study in patients who had been receiving treatment with imiglucerase at dosages ranging from 9.5 units/kg to 60 units/kg every other week for a minimum of 2 years. Patients were required to be clinically stable and have a stable biweekly dose of imiglucerase for at least 6 months prior to enrollment. Patients were 6 to 66 years of age (mean age 42 years, including pediatric patients), and 55% were male. Imiglucerase therapy was stopped, and treatment with ELELYSO was administered every other week at the same number of units as each patient's previous imiglucerase dose. If needed, adjustment of dosage was allowed during the study in order to maintain stability of clinical parameters (i.e., spleen volume, liver volume, platelet count, and hemoglobin).

Mean (SD) organ volumes and hematologic values remained stable through 9 months of ELELYSO treatment. At baseline, spleen volume was 5.2 (4.5) MN, liver volume was 1.0 (0.3) MN, platelet count was 161,137 (73,387)/mm³, and hemoglobin was 13.5 (1.4) g/dL. After 9 months of ELELYSO treatment, spleen volume was 4.8 (4.6) MN, liver volume was 1.0 (0.2) MN, platelet count was 161,167 (80,820)/mm³, and hemoglobin was 13.4 (1.5) g/dL. ELELYSO dose remained unchanged in 30 of 31 patients. One patient required a dose increase at Week 24 (from 9.5 units/kg to 19 units/kg) for a platelet count of 92,000/mm³ at Week 22, which subsequently increased to 170,000/mm³ at Month 9.

Eighteen of the 26 adult patients who completed the 9-month clinical trial continued treatment with ELELYSO in an open-label extension trial for additional 27 months (total treatment 36 months). Patients maintained stability in clinical parameters (spleen volume, liver volume, platelet count and hemoglobin); however only 10 of 18 adult patients completed 27 months of ELELYSO treatment in the extension trial and only 7 patients had their spleen and liver volumes assessed at 36 months.

Five pediatric patients in the 9-month clinical trial who continued open-label treatment with ELELYSO for additional 24 months demonstrated stability in these clinical parameters.

16 HOW SUPPLIED/STORAGE AND HANDLING

ELELYSO is supplied as a lyophilized powder in single use vials. Each vial contains 200 units of ELELYSO.

NDC 0069-0106-01, 200 units per vial

Store ELELYSO under refrigeration at 2°C to 8°C (36°F to 46°F). Do not freeze. Protect vials from light.

As ELELYSO contains no preservative, the product should be used immediately once reconstituted. If immediate use is not possible, the reconstituted product may be stored for up to 24 hours at 2 to 8 °C (36 to 46 °F) under protection from light or up to 4 hours at 20 to 25 °C (68 to 77 °F) without protection from light. The diluted product may be stored for up to 24 hours at 2 to 8 °C (36 to 46 °F) under protection from light. Storage of the reconstituted product and the diluted product should not exceed a total of 24 hours. Do not freeze. Discard any unused product.

17 PATIENT COUNSELING INFORMATION**Hypersensitivity Reactions Including Anaphylaxis**

Advise patients and caregivers that reactions related to administration and infusion may occur during and after ELELYSO treatment, including life-threatening anaphylaxis and severe hypersensitivity reactions. Inform patients of the signs and symptoms of anaphylaxis and hypersensitivity reactions, and have them seek medical care should signs and symptoms occur. Inform patients that they should be carefully re-evaluated for treatment with ELELYSO if serious hypersensitivity reactions, including anaphylaxis, occur. Reduction of the infusion rate and/or pre-treatment with antihistamines, antipyretics and/or corticosteroids may prevent subsequent reactions [see *Warnings and Precautions (5.1)*].

Licensed from Protalix Biotherapeutics

LAB-0610-7.0

14.2 Appendix 2: Infusion Rate Algorithm

[figure not shown]
The infusion rate (IR) may be adjusted according to individual subject symptoms and signs. The assumptions with respect to adverse experiences to the infusion are:

1. Most of the subjects will tolerate the infusion without any special symptom or event. The infusion rate may be increased over time to the maximal rate 2.0 mL/minute (or 120 mL/hour) only after discussion with the Medical Monitor (an infusion duration of 1 hour).
2. Subjects presenting symptoms and signs of **severe** hypersensitivity will be evaluated according to the WHO Drug Toxicity criteria and there may be a discontinuation of treatment according to the protocol.
3. Subjects may present signs and symptoms that will respond to reducing of the infusion rate and may not appear at the next infusion.
4. Tolerability and the subject specific infusion rate will be assessed and decided by the Investigator according to vital signs and clinical status of the subject.

Definitions to be applied regarding tolerability of infusions are as follows:

Good Tolerability	Partial Tolerability	Poor Tolerability
Infusion was performed without signs and symptoms (such as burning, pruritus, flushing, discomfort, or change in vital signs).	Signs and symptoms appeared during the infusion and resolved after slowing infusion rate or at the end of the infusion.	Signs and symptoms meeting the definitions of WHO Grade 1 or 2 toxicity responding to reduction of infusion rate or responding to treatment (example, antihistamine for urticaria).

The specific algorithm to be followed is below.

14.3 Appendix 3: Taliglucerase Alfa Hypersensitivity Evaluation and Treatment Algorithm

During and after infusion of taliglucerase alfa, the following algorithm will be followed to monitor and manage the occurrence of hypersensitivity, anaphylaxis, or anaphylactoid reactions.

Clinical Signs

Early

- Sensations of warmth and itching
- Feelings of anxiety or panic

Moderate

- Pruritus
- Flushing
- Urticaria
- Chest discomfort
- Mild hypotension

Progressive

- Erythematous or massive urticarial rash
- Edema of face, neck, soft tissues

Severe

- Hypotension
- Bronchospasm (wheezing)
- Laryngeal edema (dyspnea, stridor, aphonia, drooling)
- Arrhythmias

Treatment Algorithm

With the onset of any of the above clinical signs, immediately discontinue study medication administration and initiate the following monitoring:

- Continuous electrocardiographic monitoring
- Continuous pulse oximetry
- Measure blood pressure every 5 minutes
- Perform chest auscultation every 5 minutes

- Blood samples need to be collected for Tryptase (29-33) and antibodies. Tryptase samples need to be withdrawn at:
 - 1st sample taken 0.25-3 hours after onset of symptoms
 - 2nd sample taken between 3-6 hours
 - 3rd sample taken 24-48 hours to verify the return to baseline

In the case of progressive or severe hypersensitivity, treat appropriately and withdraw the subject from the study. Treat as detailed below.

Urticaria or edema of the face, neck, or soft tissues

- Epinephrine 1:1000 solution, 0.5 mL subcutaneously, repeat as needed every 5-10 minutes
- Antihistamines
- Corticosteroids

Hypotension (systolic blood pressure (SBP) \leq 90 mmHg)

- Isotonic sodium chloride solution, 1 L every 30 minutes as needed to maintain SBP >90 mmHg
- Epinephrine 1:10,000 solution given IV at 1 μ g/minute initially, then 2-10 μ g/minute to maintain SBP >90 mmHg
- Norepinephrine 4 mg in 1 L 5% dextrose in water given IV at 2-12 μ g/minute to maintain SBP >90 mmHg
- Glucagon 1 mg in 1 L 5% dextrose in water given IV at 5-15 μ g/minute for refractory hypotension

Bronchospasm

- Oxygen by face mask at 6-8 L/minute to maintain oxygen saturation at $>90\%$
- Epinephrine 1:1000 solution, 0.5 mL subcutaneously
- Albuterol 0.5 mL of 0.5% solution in 2.5 mL of sterile saline every 15 minutes up to three doses
- Inhaled beta-agonists
- Corticosteroids

Laryngeal edema

- Epinephrine 1:1000 solution, 0.5 mL subcutaneously, repeat as needed every 5 to 10 minutes
- Corticosteroids

Premedication

Premedication for subsequent taliglucerase alfa infusions may be considered at the discretion of the Investigator and Medical Monitor for subjects experiencing early clinical signs of hypersensitivity or rash/urticaria that responds promptly to oral antihistamine administration (see also [Appendix 14.2](#) for adjustment of infusion rate). The premedication will be applied according to the following steps as needed to prevent progressive hypersensitivity:

- Antihistamine (H1 blocker: diphenhydramine, hydroxyzine, cetirizine, loratadine, desloratadine) at a standard dose 12 hours and 2 hours before the start of the infusion
- H1 blocker plus H2 blocker (ranitidine, cimetidine, famotidine) at standard doses 12 hours and 2 hours before the start of the infusion
- H1 blocker plus H2 blocker plus prednisone up to 50 mg administered 12 hours and 2 hours before the start of the infusion

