6.3.3 Removal of Subjects from Study

Reasons for permanent discontinuation include the following:

1. The subject experiences two or more Grade 3 toxicities or one or more Grade 4 toxicity considered by the Investigator associated with taliglucerase alfa treatment (see [Section 8.2.1: Adverse Events](#); and [Appendix 14.5: WHO Common Toxicity Criteria](#))
2. The subject experiences progressive hypersensitivity or severe hypersensitivity will be treated appropriately and may be withdrawn from the study, at the discretion of the treating Investigator and/or Medical Monitor (see [Appendix 14.2: Infusion Rate Algorithm](#); and [Appendix 14.3: Taliglucerase Alfa Hypersensitivity Evaluation and Treatment Algorithm](#))
3. The subject, or subject's parent or guardian, requests to discontinue treatment
4. Investigator feels that it is not in the best interest of the subject to continue treatment and/or the Investigator believes that the subject can no longer be compliant with the requirements of the study
5. Deteriorating clinical condition, which the Investigator decides additional treatments would be needed

For any discontinuation, the Investigator will obtain all required details and document the date and the main reason for the premature discontinuation. If the reason for discontinuation is an adverse event, the specific event or the main laboratory abnormality will be recorded in the case report form (CRF). The Investigator will make thorough efforts to document the outcome. The Investigator will attempt to continue to follow the subject for the full duration of the study or at least for 30 days following discontinuation. If circumstances prevent the subject from completing all visits, every attempt will be made to complete all procedures listed in [Section 9.2.11](#) for Visit 27.

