Liver	Alk phos or 5 nucleotidase	WNL	< 2.5 x N	2.6 - 5.0 x N	5.1 - 20.0 x N	> 20.0 x N
Liver	Liver- clinical	No change from baseline	-----	-----	precoma	hepatic coma
Kidney, bladder	Creatinine	WNL	< 1.5 x N	1.5 - 3.0 x N	3.1 - 6.0 x N	> 6.0 x N
Kidney, bladder	Proteinuria	No change	1 (+) or < 0.3 g% or 3 g/L	2 - 3 (+) or 0.3 - 1.0 g% or 3 - 10 g/L	4 (+) or > 1.0 g% or > 10g/L	nephrotic syndrome
Kidney, bladder	Hematuria	Negative	microscopic only	gross, no clots no Rx needed	gross and clots bladder irrigation	requires trans fusion or cystectomy
Kidney, bladder	Weight gain/ loss	< 5.0 %	5.0 - 9.9 %	10.0 - 19.9 %	20.00%	-----
Pulmonary	Pulmonary	none or no change	asymptomatic, with abnormality in PFTs	dyspnea on significant exertion	dyspnea at normal level of activity	dyspnea at rest

Category	Toxicity	Grade 0	Grade1	Grade2	Grade3	Grade4
Cardiac	Cardiac arrhythmias	none	asymptomatic, transient, requiring no therapy	recurrent or persistent, no therapy required	requires treatment	requires monitoring; or hypotension, or ventricular tachycardia or fibrillation
Cardiac	Cardiac function	none	asymptomatic, decline of resting ejection fraction by less than 20 % of baseline value	asymptomatic, decline of resting ejection fraction by more than 20 % of baseline value	mild CHF, responsive to therapy	severe or refractory CHF
Cardiac	Cardiac ischemia	none	non-specific T- wave flattening	asymptomatic, ST and T wave changes suggesting ischemia	angina without evidence of infarction	acute myocardial infarction
Cardiac	Cardiac-pericardial	none	asymptomatic effusion, no intervention required	pericarditis (rub, chest pain, ECG changes)	symptomatic effusion; drainage required	tamponade; drainage urgently required
Cardiac	Hypertension	none or no change	asymptomatic, transient increase by greater than 20 mm Hg (D) or to > 150 / 100 if previously WNL. No treatment required.	recurrent or persistent increase by greater than 20 mm HG (D) or to > 150 / 100 if previously WNL. No treatment required.	requires therapy	hypertensive crisis
Cardiac	Hypotension	none or no change	changes requiring no therapy (including transient orthostatic hypotension)	requires fluid replacement or other therapy but not hospitalization	requires therapy and hospitalization; resolves within 48 hours of stopping the agent	requires therapy and hospitalization for > 48 hrs after stopping the agent

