Neurologic	Neuro: sensory	none or no change	mild paresthesia; loss of deep tendon reflexes	mild or moderate objective sensory loss moderate paresthesia	severe objective sensory loss or paresthesia that interfere with function	-----
Neurologic	Neuro: motor	none or no change	subjective weakness; no objective findings	mild objective weakness without significant impairment of function	objective weakness with impairment of function	paralysis

Category	Toxicity	Grade 0	Grade 1	Grade 2	Grade 3	Grade 4
Neurologic	Neuro: cortical	none	mild somnolence or agitation	moderate somnolence or agitation	severe somnolence, (>50% waking hours), agitation, confusion, disorientation or hallucinations	coma, seizures, toxic psychosis
Neurologic	Neuro: cerebellar	none	slight incoordination, dysdiadochokinesia	intention tremor, dysmetria, slurred speech, nystagmus	locomotor ataxia	cerebellar necrosis
Neurologic	Neuro: mood	no change	mild anxiety or depression	moderate anxiety or depression	severe anxiety or depression	suicidal ideation
Neurologic	Neuro: headache	none	mild	moderate or severe but transient	unrelenting and severe	-----
Neurologic	Neuro: constipation	none or no change	mild	moderate	severe	ileus > 96 hrs
Neurologic	Neuro: hearing	none or no change	asymptomatic, hearing loss on audiometry only	tinnitus	hearing loss interfering with function but correctable with hearing aid	deafness not correctable
Neurologic	Neuro: vision	none or no change	-----	-----	symptomatic subtotal loss of vision	blindness
Pain	Pain	none	mild	moderate	severe	requires narcotics
Skin	Skin	none or no change	scattered macular or papular eruption or erythema that is asymptomatic	scattered macular or papular eruption or erythema with pruritus or other associated symptoms	generalized symptomatic macular, papular or vesicular eruption	exfoliative dermatitis or ulcerating dermatitis
Alopecia	Alopecia	no loss	mild hair loss	pronounced or total hair loss	-----	-----

Category	Toxicity	Grade 0	Grade 1	Grade 2	Grade 3	Grade 4
Allergy	Allergy	none	transient rash, drug fever < 38°C (100.4°F)	urticaria, drug fever 38°C (100.4°F), mild bronchospasm	serum sickness, bronchospasm requiring parenteral medication	anaphylaxis
Local	Local	none	pain	pain and swelling with inflammation or phlebitis	ulceration	plastic surgery indicated

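### A mild wheeze or a transient arrhythmia is a withdrawal event under Protocol Appendix 14.3, but a WHO Grade 1 or 2 sign that Appendix 14.2 can place in an infusion-tolerability class

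*Protocol*

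**What the plan says.** Five places in the protocol bear on what follows an infusion reaction.

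- **Appendix 14.3** sorts clinical signs into Early, Moderate, Progressive and Severe. The Severe group includes "Bronchospasm (wheezing" and arrhythmias, neither limited by intensity, duration or need for treatment. It then instructs: "In the case of progressive or severe hypersensitivity, treat appropriately and withdraw the subject from the study".
- **Appendix 14.5** (WHO criteria) grades by intensity. In the Allergy row, "mild bronchospasm" is Grade 2 and "bronchospasm requiring parenteral medication" is Grade 3. In the Cardiac arrhythmias row, "asymptomatic, transient, requiring no therapy" is Grade 1.
- **Section 6.3.3 item 1** makes toxicity grade a reason for discontinuation: "The subject experiences two or more Grade 3 toxicities or one or more Grade 4 toxicity", where the investigator judges it related to the drug. It cites 14.5.
- **Section 6.3.3 item 2**, like the Synopsis, leaves withdrawal for progressive or severe hypersensitivity to the investigator or medical monitor. It cites both 14.2 and 14.3.
- **Appendix 14.2** says that subjects with severe hypersensitivity "will be evaluated according to the WHO Drug Toxicity criteria" and that discontinuation may follow. It labels as Poor Tolerability those Grade 1 or 2 signs that respond to a reduced rate or to treatment.

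SAP 6.7.1 reuses the sign groups of Appendix 14.3 as reporting headings.

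**The concern.** Two severity scales are applied to the same reaction, and the protocol does not map one onto the other. Appendix 14.3 classifies by the kind of sign and Appendix 14.5 by its intensity. For the milder forms of a sign that 14.3 calls Severe, they point in different directions.

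This differs from the question of whether withdrawal is mandatory or discretionary. Item 2 of Section 6.3.3 gives discretion only once a reaction counts as progressive or severe, and the two appendices it cites do not agree on when that is. Replacing an instruction to withdraw by permission to withdraw would leave the classification open.

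At stake is consistent handling of subjects across sites. The trial enrols up to 15 subjects to obtain at least 9 completers, so sites need one reading of the rule.

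**Working it through.** The plan gives no figure on this point, so there is nothing numerical to reproduce. The check takes each sign, reads its group in 14.3 and its grade in 14.5, and applies Section 6.3.3 item 1 as a rule: met if (number of related Grade 3 toxicities ≥ 2) or (number of related Grade 4 toxicities ≥ 1).

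| Sign | 14.3 group | 14.5 grade | Item 1 met by this event alone? |
|---|---|---|---|
| Mild bronchospasm | Severe | 2 (Allergy) | No |
| One bronchospasm needing parenteral medication | Severe | 3 (Allergy) | No; two are needed |
| Asymptomatic transient arrhythmia, untreated | Severe | 1 (Cardiac) | No |
| Recurrent or persistent arrhythmia, untreated | Severe | 2 (Cardiac) | No |
| Mild bronchospasm with transient arrhythmia | Severe | 2 and 1 | No |
| Arrhythmia that needs monitoring | Severe | 4 (Cardiac) | Yes |

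**Step 1.** For mild bronchospasm and for a transient arrhythmia, 14.3 directs withdrawal and the grade rule is not triggered.

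**Step 2.** The protocol itself links the scales. Appendix 14.2 sends severe hypersensitivity to the WHO criteria and also defines a tolerability class by WHO Grade 1 or 2. A Grade 2 wheeze that responds to treatment fits that class, as does a Grade 1 arrhythmia that settles when the rate is reduced. Both are listed as Severe in 14.3.

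**Step 3.** Item 2 of Section 6.3.3 points the site to 14.2 and 14.3 together, without saying which governs.

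**Step 4.** The grade can also depend on following 14.3. That appendix lists subcutaneous epinephrine for bronchospasm and continuous electrocardiographic monitoring at the onset of any sign. In 14.5, bronchospasm needing parenteral medication is Grade 3 and an arrhythmia needing monitoring is Grade 4. Nothing says whether the grade is assigned before or after these measures.

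**Hypotension is not a clean example.** In 14.5, hypotension that "requires fluid replacement or other therapy but not hospitalization" is Grade 2. But 14.3 is tiered here: mild hypotension is in the Moderate group, and its treatment list gives a systolic limit of 90 mmHg. The finding therefore rests on bronchospasm and arrhythmia.

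**The case against.** The strongest reply is that the reasons in Section 6.3.3 are alternatives. Appendix 14.5 only grades; it holds no rule to continue or withdraw. A reader might infer that a subject with a mild wheeze is withdrawn under one table and must continue under the other. The documents do not say that: missing the item 1 threshold keeps nobody on treatment, because item 2 permits withdrawal whatever the WHO grade. This stands, and it limits the finding to an unresolved classification.

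Second, 14.2 can be read as a sequence: recognise a severe sign, then grade it. On that reading the WHO grade does not define severe. The reading is possible, but it does not say what follows when a sign listed as Severe is then graded 1 or 2, which is the gap. The only treatment example 14.2 gives for its Grade 1 or 2 class is an antihistamine for urticaria, and its algorithm figure is not shown in the available text, so its later steps cannot be checked.

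Third, the overlap is narrow. The arrhythmia row in 14.5 is a general cardiac row rather than an allergy row, and the measures in 14.3 may themselves raise the grade. Both points stand. Mild bronchospasm, in the Allergy row, remains the clearest case.

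**Conclusion.** The inconsistency is real and small in scope: the milder forms of two signs have no single class, and the passages a site would consult do not settle the consequence. It is a safety-instruction and consistency matter worth correcting. The conclusion assumes that the WHO criteria named in 14.2 are the table in 14.5, that the unqualified terms in 14.3 mean what they say, and that the missing figure in 14.2 does not already resolve the matter.

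Three larger consequences that a reader might infer are not supported.

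- **Frequency.** The appended label reports hypersensitivity in 21 of 72 patients (29%), but that covers all signs, including pruritus, flushing and rash. Its 2 of 72 (3%) for anaphylaxis is not the conflict rate either. How often these two signs would occur in mild form is not given.
- **Efficacy result.** One might suppose that an early withdrawal counts as a non-responder and could tip the responder-rate criterion in SAP 6.1.2. The plan does not score withdrawals that way. Section 6.3.3 seeks continued follow-up. SAP 5.3 uses the early-termination MRI, then possibly ultrasound, and carries baseline forward only if there is no post-baseline imaging. That analysis is also supplementary, and no effect on the primary Wilcoxon test is shown.
- **Reporting.** One might expect two severity accounts in the report to contradict each other. No WHO-graded adverse event table is planned. Intensity is scored mild, moderate or severe by effect on usual activity, and SAP 6.7.1 uses the 14.3 groups only as headings for preferred terms.

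**What to change.** Reconcile the discontinuation list in the Synopsis, Section 6.3.3 and Appendices 14.2, 14.3 and 14.5 so that each sign has one class and one stated consequence. A single cross-reference table would do this, giving for each sign its 14.3 group, its 14.5 grade or range of grades, its 14.2 tolerability class where one applies, and the resulting action. It should state whether the grade is assigned before or after the monitoring and treatment in 14.3. Section 6.3.3 item 2 should then cite that table.

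The same amendment should settle the difference between the instruction to withdraw in 14.3 and the permission to withdraw in the Synopsis and Section 6.3.3. The SAP 6.7.1 headings should be matched to the result. Which class and which consequence apply is for the clinical team.

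The cost is amendment wording, one table and a matching edit to the SAP headings. It needs no new data and no change to the sample size or analyses.

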5 WARNINGS AND PRECAUTIONS

5.1 Hypersensitivity Reactions Including Anaphylaxis

Serious hypersensitivity reactions, including anaphylaxis, have occurred in some patients treated with ELELYSO. In clinical trials, 2 of 72 (3%) patients treated with ELELYSO experienced signs and symptoms consistent with anaphylaxis. Signs and symptoms of these patients included urticaria, hypotension, flushing, wheezing, chest tightness, nausea, vomiting, and dizziness. These reactions occurred during ELELYSO infusion.

In clinical trials with ELELYSO, 21 of 72 (29%) patients experienced hypersensitivity reactions, including anaphylaxis. Signs and symptoms of hypersensitivity reactions included pruritus, angioedema, flushing, erythema, rash, nausea, vomiting, cough, chest tightness, and throat irritation. These reactions have occurred up to 3 hours after the start of infusion [see *Adverse Reactions (6.1)*].

Due to the potential for anaphylaxis, appropriate medical support should be readily available when ELELYSO is administered. Observe patients closely for an appropriate period of time after administration of ELELYSO, taking into account the time to onset of anaphylaxis seen in clinical trials. Inform patients of the signs and symptoms of anaphylaxis, and instruct them to seek immediate medical care should signs and symptoms occur. If anaphylaxis occurs, ELELYSO should be immediately discontinued, and appropriate medical treatment should be initiated. Management of hypersensitivity reactions should be based on the severity of the reaction and include slowing or temporary interruption of the infusion and/or administration of antihistamines, antipyretics, and/or corticosteroids for mild reactions. Pretreatment with antihistamines and/or corticosteroids may prevent subsequent hypersensitivity reactions. Patients were not routinely premedicated prior to infusion of ELELYSO during clinical studies. If severe hypersensitivity reactions occur, immediately stop the infusion of ELELYSO and initiate appropriate treatment.

Consider the risks and benefits of re-administering ELELYSO in patients who have experienced a severe reaction associated with ELELYSO. Caution should be exercised upon rechallenge, and appropriate medical support should be readily available [see *Adverse Reactions (6.3)*].

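### Appendix 14.3 stops the infusion at any listed sign, while Appendix 14.2 presupposes slowing or completing it for the same signs, and no printed text says which governs

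*Protocol*

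**What the plan says.** **Protocol Appendix 14.3.** For the period during and after infusion, "the following algorithm will be followed to monitor and manage the occurrence of hypersensitivity, anaphylaxis, or anaphylactoid reactions". Signs are listed in four grades. Early covers warmth, itching, anxiety and panic. Moderate covers pruritus, flushing, urticaria, chest discomfort and mild hypotension. Progressive and Severe follow. The order after the list does not distinguish between grades: "With the onset of any of the above clinical signs, immediately discontinue study medication administration and initiate the following monitoring". The monitoring is continuous ECG and pulse oximetry, blood pressure and chest auscultation every 5 minutes, and blood for antibodies and three timed tryptase samples.

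**Protocol Appendix 14.2.** "The infusion rate (IR) may be adjusted according to individual subject symptoms and signs", with the subject's rate decided by the Investigator. One stated assumption is that "Subjects may present signs and symptoms that will respond to reducing of the infusion rate and may not appear at the next infusion". Three tolerability classes are defined:

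- Good: "Infusion was performed without signs and symptoms (such as burning, pruritus, flushing, discomfort, or change in vital signs".
- Partial: "Signs and symptoms appeared during the infusion and resolved after slowing infusion rate or at the end of the infusion".
- Poor: "Signs and symptoms meeting the definitions of WHO Grade 1 or 2 toxicity responding to reduction of infusion rate or responding to treatment", with an antihistamine for urticaria as the example.

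The text then refers to an algorithm in a figure, which is not shown.

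**Protocol Appendix 14.1, label section 5.1.** Management is graded by severity. The options "include slowing or temporary interruption of the infusion and/or administration of antihistamines, antipyretics, and/or corticosteroids for mild reactions". An immediate stop is described for anaphylaxis and severe reactions.

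**Cross-references.** Section 6.3.3, item 2, cites Appendices 14.2 and 14.3 together, on withdrawal after progressive or severe reactions. The premedication paragraph of Appendix 14.3 points to Appendix 14.2 for rate adjustment, in the context of later infusions. Section 7.4 cites Appendix 14.2 on raising the rate.

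**The concern.** A nurse who sees flushing 20 minutes into an infusion has two printed sources. One requires administration to stop and intensive monitoring to begin. The other classifies the event by what happened after the rate was reduced, or by whether the sign had gone when the infusion finished. The second description assumes an infusion that was still running.

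The first stake is patient handling: this is a bedside instruction for possible hypersensitivity, in a trial open to subjects of any age, with a product whose label reports anaphylaxis. The second is the safety record. SAP section 6.6.2 counts temporary discontinuations and dose reductions due to adverse events, section 6.6.3 lists and summarizes dosing, and section 6.7.1 tabulates hypersensitivity signs under the Appendix 14.3 grades. Tolerability also feeds later decisions: Section 7.4 makes a rate increase depend on it, the Synopsis and Section 6.1 allow home treatment only after at least 3 uneventful infusions, and SAP section 3.5.3 ties the frequency of vital-sign checks to whether previous infusions were tolerated.

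**Working it through.** The point rests on no calculated figure in the plan, so the check is a comparison of texts. The sample-size calculation is not an input and is not affected.

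**Step 1. Signs in both appendices.**

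| Sign | Appendix 14.3 | Appendix 14.2 | Match |
|---|---|---|---|
| Pruritus | Moderate (itching also Early) | Named under Good | By name |
| Flushing | Moderate | Named under Good | By name |
| Urticaria | Moderate | Example under Poor | By name |
| Discomfort | Moderate, chest only | Named, unspecified | Similar |
| Blood pressure fall | Moderate (mild hypotension) | Change in vital signs | By inference |
| Burning | Not listed | Named under Good | None |

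Three signs match by name, and the rest of the argument needs only those.

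**Step 2. Action for a shared sign, infusion in progress.**

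| Source | Action | Strength |
|---|---|---|
| Appendix 14.3 | Stop at onset and start the monitoring set | Mandatory |
| Appendix 14.2, printed text | Slow, or let the infusion finish | Permissive; presupposed by the definitions |
| Label 5.1, mild reactions | Slow or temporarily interrupt, and/or give medication | Advisory |

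Under Appendix 14.3 as printed, pruritus, flushing or urticaria leads to a stop, and slowing a running infusion is not offered. Under the Partial definition, the same sign may be met by slowing or may persist until the end of the infusion.

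**Step 3. Is there a rule of precedence?** Section 6.3.3 cites both appendices without ranking them and concerns withdrawal. The only link from 14.3 to 14.2 concerns subsequent infusions. Section 7.4 addresses the rate after a well-tolerated infusion. None of these settles the infusion in progress. Nor does any printed text say whether the stop is temporary or whether restart is allowed.

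**Step 4. Are Partial and Poor exclusive?** Appendix 14.5 places urticaria under Allergy Grade 2. Urticaria that clears on slowing therefore meets Partial (resolved after slowing) and Poor (Grade 1 or 2, responding to rate reduction). Any Grade 1 or 2 sign that clears on slowing does the same.

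**Step 5. Could site habit be separated from patient differences?** Appendix 14.4 gives 9 subjects at 5 to 10 sites: 9/10 = 0.9 to 9/5 = 1.8 per site. With the Synopsis ceiling of 15 it is 15/10 = 1.5 to 15/5 = 3.0. Differences in handling could not be separated from differences between patients.

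**Step 6. Can the size be derived?** No.

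- *Subjects affected.* The label reports hypersensitivity in 21 of 72 patients: 21/72 = 29%, and 0.29 × 9 = 2.6, 0.29 × 15 = 4.4. This does not count subjects who would meet the conflict. The 29% covers all severities, including anaphylaxis. It includes nausea, vomiting, cough and throat irritation, which Appendix 14.3 does not list, and reactions up to 3 hours after the start of infusions that last 1 to 2 hours under Section 7.4. This trial also excludes subjects with any food or drug allergy history. Of the 2 reactors among 9 treatment-naïve children, one had severe vomiting and gastrointestinal inflammation, which are not listed signs.
- *Delivered dose.* One infusion lost entirely is 1/27 = 3.7% of the planned infusions. How often part or all of an infusion would be lost is unknown.

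**The case against.** The strongest reply is that the two appendices do different jobs. Appendix 14.2 issues no within-infusion order in its printed text: the rate may be adjusted, the Investigator decides, and Partial and Poor are labels applied to an infusion. If the stop in Appendix 14.3 is a pause, restarting at a lower rate might satisfy both, and the label itself lists temporary interruption beside slowing. Poor also covers signs that respond to treatment, which fits a stop. The missing figure may contain a stop or restart step.

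Much of this stands, and it limits what can be claimed. A reader might infer four stronger things that the documents do not support:

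- That Appendix 14.2 orders the infusion to be slowed and continued. It presupposes this and does not order it.
- That a site following Appendix 14.3 delivers a partial dose. That requires no restart, which is not stated.
- That the Partial/Poor overlap leads to different rates at the next infusion. No printed text assigns a next rate to either class.
- That about 3 of 9 or 4 of 15 subjects would meet the conflict. The 29% rate does not measure that.

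The reply does not remove the inconsistency. The pause reading is nowhere printed. A sign that resolves only at the end of the infusion is hard to square with a stop at onset even if restart is allowed. Appendix 14.3's monitoring and tryptase sampling have no counterpart in the printed text of Appendix 14.2, so handling differs whichever way the stop is read.

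**Conclusion.** The inconsistency is real and lies in the current text. For pruritus, flushing and urticaria, Appendix 14.3 requires an immediate stop with intensive monitoring, while Appendix 14.2's definitions presuppose an infusion that is slowed or completed. Precedence, the meaning of the stop and restart are all unstated, and Partial and Poor overlap. The consequence that follows is that handling and recording (interruptions, tolerability class) could differ by site for the same sign.

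The size cannot be quantified from the documents. No effect on the primary endpoint is shown. Full analysis set membership does not change when an adverse event cuts a dose short (Section 10.2; SAP section 4), and power is unaffected. The case for acting rests on patient safety and clean safety data.

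The conclusion rests on the printed text. It assumes that the unseen Appendix 14.2 figure does not resolve the matter, and this must be checked. It concerns the action on early and moderate signs during an infusion, and does not address withdrawal after progressive or severe reactions.

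**What to change.** The sponsor and Medical Monitor should check the Appendix 14.2 figure, then reconcile Appendices 14.2 and 14.3, and their relation to the label text in Appendix 14.1, so that the protocol:

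1. gives each overlapping sign one stated infusion action;
2. says whether the stop in Appendix 14.3 is temporary and whether restart is allowed;
3. states which appendix governs the infusion in progress;
4. defines Partial and Poor so that no event meets both.

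Which action applies to which sign, and where the line between the classes falls, is for them to decide.

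The cost is a protocol amendment to two appendices and notice to sites. It needs no added subjects, procedures or change to the statistical analysis.
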